- 2) The recruitment of a sub-sample of 60 participants who live in Winnipeg, MB which will be drawn from the larger sample of 300 participants and by advertisement. In addition to completing all the components listed above from the recruitment of 300 participants, they will be also asked to wear a physical activity monitor, called an accelerometer.

Inclusion and exclusion criteria

Inclusion criteria:

- Male and female employees 18-70 years old
- Self-identify as being physically inactive in the last 3 months (less than 150 minutes of moderate-vigorous physical activity per week)
- Ready to adopt a more physically active lifestyle based on the Transtheoretical Model¹⁰
- Specific to the sub-sample of 60 participants: Live in Winnipeg, MB

Exclusion criteria:

- Individuals who do not have a personal mobile phone
- Any physical limitations that would not allow a person to engage in physical activity
- Any cognitive limitations that would not allow a person to consent for the study
- Specific to the sub-sample of 60 participants: Those who live outside of Winnipeg, MB.

To our knowledge, no characteristics of the participants make them especially vulnerable or require extra precautions to administer the user observation study. Participants will be healthy volunteers able to provide informed consent.

Participant recruitment

Recruitment of participants involves two phases (Figure 1):

- 1) Recruitment of 300 individuals who download the ENCOURAGE App the iTunes Store or Google play and choose to enroll in the study. Users will be asked via a textbox to determine if they wish to participate in a research project. A description of the project, as well as an electronic consent form will be provided prior to enrolment through Survey Monkey. In order to track participants in the study, we will be asking for their e-mail addresses, their date of birth, and first and last name initials.

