- 2) Recruitment of 60 individuals who live in Winnipeg, MB to wear an accelerometer. We will employ a convenience sampling approach, where participants who are already using the App and participating in the study (i.e., the 300 participants described above) will be asked to participate if they live in Winnipeg. Additionally, we will employ a convenience sampling approach at the St. Boniface Hospital, University of Manitoba, and Tactica Interactive. Participants will be contacted via e-mail. First, we will use an e-mail approach to contact participants. The e-mail approach will provide contact information for potential participants to reach research staff to facilitate the recruitment and consent of participants at a mutually agreeable location. Secondly, we will use a poster advertisement approach (**Appendix 7**) to facilitate recruitment. Posters will be placed around the St. Boniface Hospital, University of Manitoba, and Tactica Interactive. In total for the sub-study, more than 12,000 staff members at the St. Boniface Hospital, 8,700 faculty/staff, at the University of Manitoba, and Tactica Interactive will be accessible, including:
 - Nurses and Nurse Practitioners;
 - Physicians;
 - Property Management (electrical, carpentry, mechanical);
 - Administrators and clerical support staff; and,
 - Researchers
 - Software developers

Study procedures

Large study procedures:

After participants choose to participate in the study, participants will be asked to complete a series of questionnaires at baseline, one week and every month for a total of six months (i.e., 8 different

occasions). The questionnaires (**Appendix 8**) will take approximately 30-45 minutes to complete and comprise of the following:

- 1) Demographics
- 2) Depressive symptoms with the Patient Health Questionnaire-9
- 3) Physical activity using the Godin Leisure Time Exercise Questionnaire
- 4) Cardiovascular health risk using the Cardiovascular Health in Ambulatory Care Research Team (CANHEART) questionnaire
- 5) Occupational Sitting with the Occupational Sitting and Physical Activity Questionnaire
- 6) Self-efficacy levels for physical activity and reducing sedentary time with the Exercise Self-Efficacy Questionnaires and Self-Regulatory Efficacy to Manage Sedentary Behavior questionnaire
- 7) Confidence levels for reducing sedentary behaviors with the Barrier Self-Efficacy to Reduce Sedentary Behavior and Self-efficacy to Reduce Total Daily Sedentary Time questionnaires.

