- 8) Physical activity levels at the workplace with the Workplace Sitting Breaks Questionnaire

Research participants will be prompted within the App to a hyperlink to complete the research questionnaires on Survey Monkey. In order to track individual research participant responses The links are as follows:

- 1) Description of the study/eligibility form, consent to participate, and baseline questionnaire: <https://www.surveymonkey.com/r/L3KDHRQ>
- 2) 1 week survey: <https://www.surveymonkey.com/r/L39CZB5>
- 3) 1 month survey: <https://www.surveymonkey.com/r/L3J2M67>
- 4) 2 month survey: <https://www.surveymonkey.com/r/L3SKXGH>
- 5) 3 month survey: <https://www.surveymonkey.com/r/L3MDLCF>
- 6) 4 month survey: <https://www.surveymonkey.com/r/L3FLMWG>
- 7) 5 month survey: <https://www.surveymonkey.com/r/L3B28KX>
- 8) 6 month survey: <https://www.surveymonkey.com/r/L3P9FGC>

[figure not shown]
Participants will also be asked on two separate occasions over the 6 month period to document their experiences using an experience sampling approach. A list of questions used are in **Appendix 5**.

Sub-study procedures:

Participants from Winnipeg, MB who choose to enroll in the sub-study will complete the study procedures for the large study and will also be asked to meet with research staff to obtain consent for the smaller study and will be asked to wear an accelerometer for 7-day periods at baseline and every month for 6 months (i.e., 7 different occasions). The research appointments will last approximately 30 minutes each.

See below for a figure overviewing the flow of the study.

Figure 1. Study flow chart

Assessment of Safety

Since this is not a drug study, rescue medication is not warranted. Should any participant experience adverse effects as a consequence of participation in the study, they will be excluded from the study and receive routine clinical care. All serious adverse events as well as death due to any cause or cardiovascular death will be reviewed by the medical monitor within 24 hrs of becoming aware of events. Any Serious Adverse Events will be reported to the University of Manitoba Health Ethics Boards and St. Boniface Hospital.

Statistics

Sample Size

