Appendix 7: Poster advertisement

ENCOURAGE Researchers need your help!!!

Sedentary behaviour is becoming increasingly common in the modern working environment. This is concerning, as researchers are beginning to recognize that sitting for extended periods of time increases your risk of diabetes, cardiovascular disease and other adverse health outcomes. Unfortunately, sitting at work is often unavoidable, but we want you to help us change that!

We are seeking volunteers for a research study to test the public release of a mobile app that is designed to decrease sedentary time in the workplace

Are you?

[figure not shown]
- Between the ages of 18 and 70
- An employee of the University of Manitoba or St. Boniface Hospital with a fairly inactive job?
- Consider yourself physically inactive but ready to make a change towards a more active lifestyle?

If you are eligible, seven study visits will be scheduled over 6 months that will include:

- Installing the ENCOURAGE App on your mobile phone (first visit only)
- Wearing a device called an accelerometer to measure your physical activity behavior
- Complete a series of questions regarding your lifestyle behaviors and cardiovascular health risk

You will also be asked to complete weekly questions regarding your experience with the App

If you are interested, please contact us at [contact].

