Appendix 8: Study questionnaire package

Appendix List of questionnaires

1. Demographics Questionnaire
2. Patient Health Questionnaire-9
3. Occupational Sitting and Physical Activity Questionnaire
4. Godin leisure time exercise questionnaire
5. The Cardiovascular Health in Ambulatory Care Research Team (CANHEART) health questionnaires
 - CANHEART Questionnaire – Tobacco use
 - CANHEART Questionnaire – Fruit and vegetable consumption
 - CANHEART Questionnaire – High blood pressure
 - CANHEART Questionnaire – Diabetes
6. Exercise Self-Efficacy Questionnaires:
 - Physical Activity Task Self-Efficacy Questionnaire
 - Physical Activity Self-Regulatory Efficacy Questionnaire
7. Self-Regulatory Efficacy to Manage Sedentary Behavior
8. Barrier Self-Efficacy to Reduce Sedentary Behavior
9. Self-efficacy to Reduce Total Daily Sedentary Time
10. Workplace Sitting Breaks Questionnaire

PHQ-9 QUESTIONNAIRE

Over the past 2 weeks, how often have you been bothered by any of the following problems? Please circle the best response, according to the following scale:

	0	1	2	3
	Not at all	Several days	More than half the days	Nearly every day
	Not at all	Several days	More than half the days	Nearly every day
1. Little interest or pleasure in doing things	0	1	2	3
2. Feeling down, depressed or hopeless	0	1	2	3
3. Trouble falling or staying asleep, or sleeping too much	0	1	2	3
4. Feeling tired or having little energy	0	1	2	3
5. Poor appetite or overeating	0	1	2	3
6. Feeling bad about yourself – or that you are a failure or have let yourself or your family down	0	1	2	3
7. Trouble concentrating on things, such as reading the newspaper or watching television	0	1	2	3
8. Moving or speaking so slowly that other people could have noticed. Or the opposite – being so fidgety or restless that you have been moving around a lot more than usual	0	1	2	3
9. thoughts that you would be better off dead, or of hurting yourself in some way	0	1	2	3
10. If you checked off any problems, how difficult _____ have these problems made it for your to do your _____ work, take care of things at home, or get along _____	Not difficult at all Somewhat difficult Very difficult			

with other people?

Extremely difficult

please check (✓) your response

OCCUPATIONAL SITTING AND PHYSICAL ACTIVITY QUESTIONNAIRE (OSPAQ)

1. How many hours did you work in the last 7 days? _____ hours
2. During the last 7 days, how many days were you at work? _____ days

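### PHQ-9 item 9 on self-harm goes out by web link at up to eight occasions, and the available text does not say who reads a positive answer or when: show crisis resources directly after it, or use the eight-item form

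*Protocol*

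**What the plan says.** The protocol's large-study procedures list "Depressive symptoms with the Patient Health Questionnaire-9" as the second instrument in the package. Participants are to "complete a series of questionnaires at baseline, one week and every month for a total of six months", which the protocol counts as eight occasions. Delivery is remote: participants are "prompted within the App to a hyperlink to complete the research questionnaires on Survey Monkey", and eight survey links are listed. Appendix 8 prints the PHQ-9 in full, including the item on "thoughts that you would be better off dead, or of hurting yourself in some way", scored 0 to 3.

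Assessment of Safety has two provisions:
- A participant harmed by taking part leaves the study and receives routine care.
- Serious adverse events and deaths "will be reviewed by the medical monitor within 24 hrs of becoming aware of events".

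Risk and Benefits names the risk of physical activity and the limits of confidentiality. It does not mention distress or answers about self-harm. The exclusion criteria do not screen for depression or self-harm thoughts.

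**The concern.** The study asks about self-harm thoughts repeatedly and at a distance, but the available text sets no path from a positive answer to a person who will see it. The 24-hour review does not supply one. It concerns serious adverse events and deaths, which a questionnaire answer is not, and its clock starts when staff learn of an event. If nobody has the task of looking, the clock need never start.

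What is at stake is participant safety, not an estimate or a test. A participant may disclose such thoughts and reasonably expect that someone on the team will see the answer. If the plan is followed as written, the answer can sit unread.

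**Working it through.** **Occasions.** Baseline (1) + one week (1) + months 1 to 6 (6) = 8. This reproduces the protocol's own count and matches the eight survey links.

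**Times item 9 can be asked, if every form is returned.**
- 300 participants × 8 = 2,400.
- The sub-sample of 60 is "drawn from the larger sample of 300 participants and by advertisement", so some of the 60 may come on top of the 300. If all do, (300 + 60) × 8 = 360 × 8 = 2,880.
- With dropout the number is lower. Assume linear loss to a fraction r retained at month 6, with occasions at t = 0, 0.25, 1, 2, 3, 4, 5 and 6 months. Forms = 300 × [8 − (1 − r) × 21.25 / 6], because the times sum to 21.25. For r = 0.5 this is about 1,870, and for r = 0.25 about 1,600. Both retention values are assumptions.

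**Positive answers.** The documents give no rate. Assume 0.5% to 5% of forms.
- Of 2,400 forms: 0.005 × 2,400 = 12, up to 0.05 × 2,400 = 120.
- Of 2,880 forms: 0.005 × 2,880 ≈ 14, up to 0.05 × 2,880 = 144.
- At least one positive among 300 baseline forms, if answers are independent: 1 − 0.995^300 = 78% at 0.5%, and 1 − 0.99^300 = 95% at 1%.

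These figures show only that a positive answer is a realistic event, even at a low rate. They do not estimate how many there will be.

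**Delay before an answer is read.** Unknown. It is near zero if returns are read as they arrive. For a baseline answer it is about 26 weeks (six months) if forms are first read after that participant's last survey, and longer if they are read only after the last participant finishes.

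**Who would see an answer.** Set side by side, the relevant sections give:
- Study procedures: how forms are sent, but not who reads them.
- Assessment of Safety: what happens after staff know of a serious event, but not how a questionnaire answer becomes known.
- Participant recruitment: e-mail address, date of birth and initials are collected. Staff therefore have a contact route, but no stated duty to use it.

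No threshold, reader, time limit, automatic message or referral step appears in any of them.

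**Effect of dropping item 9 on the score and the analysis.** Nine items scored 0 to 3 give a maximum of 9 × 3 = 27; eight give 8 × 3 = 24. The two objectives concern physical activity and cardiovascular risk. The protocol's sample size rests on moderate-vigorous physical activity, and the SAP's primary outcome is breaks in sedentary time. None of these uses the PHQ-9. It is probably one of the SAP's secondary continuous measures, although the SAP does not name it.

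**The case against.** The strongest reply is that this argues from absence. A crisis notice would most naturally sit in the consent form or on the survey page itself, and neither was visible. The protocol also requires ethics-board and hospital review before the study starts, and the board reviews the consent form. This stands as far as it goes: a notice may exist, and the point is limited to the available text. Review by a board does not show that a procedure exists, however. A notice to participants would also not say who on the team reads the answers, which belongs in the safety section.

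A second reply is that deleting the item makes nobody safer, because a person with such thoughts still has them. That is correct. Omission removes an unanswered disclosure, not the risk behind it. A reader might infer that deletion is the one proper remedy, but the documents do not support that. Fixed text after the item offers the respondent something, keeps the nine-item instrument and needs no staff.

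A reader might also infer that sub-study participants are protected by their visits and that exposure can be measured by the forms falling outside a visit. The documents do not support this either. The poster says that visits include the task "Complete a series of questions regarding your lifestyle behaviors and cardiovascular health risk", which does not name mood, and nothing says that PHQ-9 answers are read at an appointment. A visit does give staff a contact route beyond e-mail, but a contact route is not a reading procedure.

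**Conclusion.** The point holds as a gap in the available text with an inexpensive remedy. Item 9 can be asked up to 2,400 times, or 2,880 if the whole sub-sample is additional, assuming full recruitment and full return. No one is assigned to read the answers, and the one timed safety review neither covers them nor starts without prior awareness. The rate of positive answers and the reading delay are unknown, so the harm cannot be sized. The 12 to 144 positive forms rest wholly on the assumed 0.5% to 5%.

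A reader might go further and conclude that answers will go unread or that participants are given no crisis information. The documents do not establish that, because the consent pages and live surveys could contain a notice or a procedure. Confidence is therefore medium. The change should be made unless the team can point to text that already does the job.

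**What to change.** Either of two changes closes the main gap without extra staff.

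1. **Keep item 9 and add a notice.** Unless already present, show fixed crisis-resource text to every respondent directly after item 9 in all eight surveys, and state that answers are not monitored in real time. Showing it to everyone means that nothing depends on detecting a positive answer. The cost is a few lines of survey text.
2. **Drop item 9** if the team will not read answers promptly. Use the eight-item score (0 to 24) and change the instrument's name and scoring throughout. The cost is the loss of the standard nine-item total (0 to 27) and of the self-harm information. The underlying risk is not reduced.

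Neither option alters an objective, the primary outcome or the sample size.

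If a reading procedure already exists, cite it in Assessment of Safety with the responsible role and the time limit. Creating one now would give more protection than a notice alone, but it is not a small change: someone would have to screen up to 2,400 to 2,880 forms, with weekend cover, and pass positive answers to the medical monitor as a new duty. The wording of the notice and any clinical response are for the medical monitor and the ethics board.

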
Trial objectives and purpose

The objectives of this study are to determine if the final product ENCOURAGE App can over a 6 month period:

- 1) Enhance physical activity levels; and,
- 2) Improve cardiovascular health risk;

Trial design

The public release of the ENCOURAGE App will involve two phases (Figure 1):

- 1) The recruitment of 300 individuals through the App. Any user will be able to download the ENCOURAGE App through the iTunes Store or Google Play. Note that when participants download the App, they are not automatically enrolled in the study. Participants will be prompted, after downloading the App, with a brief description of the study, as well as a pre-screening tool will be used to determine eligibility (see below for inclusion/exclusion criteria). Users will be asked via a textbox to determine if they wish to participate in a research project. Users will be asked to participate in a *time series quasi-experimental design* study to determine if the ENCOURAGE App can support participants to increase their physical activity levels over a 6 month period. The App uses a time management technique (i.e., Pomodoro technique) as a strategy to provide prompts for users to engage in an activity. The App can be customized by the users to set prompts at intervals that fits into their schedule. For example, these activities can range from a stretching activity (e.g., a neck stretch), a standing activity (e.g., stand and read), or a physical activity (e.g., fill up the printer with paper, do a squat). Additionally, the App will use Behavior Change Techniques as a way to support participants as they reduce their sedentary behavior and improve their physical activity levels.⁷ The App uses a series of Behavior Change Techniques shown to be effective in promoting a more physically active lifestyle.^{8,9} Users will also provide feedback regarding the App using an *experience sampling approach*, which uses a list of questions to guide user feedback (**Appendix 5**). Additionally, we will use *Flurry Analytics* (<http://www.flurry.com/>) to measure, track, and analyze the ENCOURAGE App performance, and aggregate-level user activity within the App. Specifically, we wish to determine the number of user sessions within the App, frequency of use, session length, user events, technical data and errors, and user geographic distribution. For a more detailed description of the experience sampling and Flurry Analytics approaches, see **Appendix 6**.

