(e.g., fast walking, baseball, tennis, easy bicycling, volleyball, badminton, easy swimming, alpine skiing, popular and folk dancing)

TIMES PER WEEK _____

c) MILD EXERCISE (MINIMAL EFFORT) (e.g., yoga, archery, fishing from river bank, bowling, horshoes, golf, snow-mobiling, easy walking)

TIMES PER WEEK _____

2. During a typical 7-Day period (a week), in your leisure time, how often do you engage in any regular activity long enough to work up a sweat (heart beats rapidly)?

OFTEN

SOMETIMES

NEVER/RARE

1.

2.

3.

CANHEART QUESTIONNAIRE – TOBACCO USE

1. Never used tobacco: 2. Ex-tobacco user: Quit date _____ 3.

Currently use:

If tobacco user, average number per day _____ and number of years _____

CANHEART QUESTIONNAIRE – FRUIT AND VEGETABLE CONSUMPTION

The next questions are about the foods you usually eat or drink. Think about all the foods you eat, both meals and snacks, at home and away from home.

1. How often do you usually drink fruit juices such as orange, grapefruit or tomato? (for example, once a day, three times a week, twice a month)

Times/day _____ OR Times/week _____

2. Not counting juice, how often do you usually eat fruit?

Times/day _____ OR Times/week _____

3. How often do you (usually) eat green salad?

Times/day _____ OR Times/week _____

4. How often do you usually eat potatoes, not including French fries, fried potatoes, or potato chips?

Times/day _____ OR Times/week _____

5. How often do you (usually) eat carrots?

Times/day _____ OR Times/week _____

6. Not counting carrots, potatoes, or salad, how many servings of other vegetables do you usually eat?

Times/day _____ OR Times/week _____

CANHEART QUESTIONNAIRE – HIGH BLOOD PRESSURE

1. We're interested in conditions diagnosed by a healthcare professional. Do you have high blood pressure? (please circle one)

Yes No

2. If yes, how old were you when you were first diagnosed?

Age in years _____

CANHEART QUESTIONNAIRE - DIABETES

1. We're interested in conditions diagnosed by a healthcare professional. Do you have diabetes? (please circle one)

Yes No

2. If yes, how old were you when you were first diagnosed?

Age in years _____

EXERCISE SELF-EFFICACY QUESTIONNAIRES**PHYSICAL ACTIVITY TASK SELF-EFFICACY QUESTIONNAIRE**

How certain are you that you can engage in moderate- to strenuous-intensity physical activity for the following durations? Please rate your degree of confidence for each duration using the scales.

10 minutes

0	1	2	3	4	5	6	7	8	9	10

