ENCOURAGE APP – statistical analysis plan:

For the primary outcome, a one-way repeated measures ANOVA or Mann-Whitney Test will be used to examine changes in the number of breaks in sedentary time from baseline to 1-month, depending if the data are normally distributed.

Other secondary, continuous outcome measures will be analyzed with a one-way repeated measures ANOVA or Mann-Whitney Test from baseline to 1 week, 1-month, 2-month, 3-month, 4-month, 5-month, and 6-month depending if the data are normally distributed. Categorical variables will be compared using a Chi-Square test. Relationships between variables will be assessed using Pearson or Spearman correlations, as well as multivariable linear or logistic regression.

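### Item 6 of the fruit and vegetable questionnaire asks for servings but is answered in times per day or week, so the unit of a recorded value cannot be recovered

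*Protocol*

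**What the plan says.** Under Trial objectives and purpose, the second of two objectives is "Improve cardiovascular health risk" over six months. Study procedures names the instrument: "Cardiovascular health risk using the Cardiovascular Health in Ambulatory Care Research Team (CANHEART) questionnaire". Appendix 8 lists four CANHEART parts: tobacco, fruit and vegetables, high blood pressure and diabetes. The diet part is "CANHEART Questionnaire – Fruit and vegetable consumption", and no other diet questionnaire is listed.

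Items 1 to 5 of that part ask for a frequency; item 2, for example, reads "Not counting juice, how often do you usually eat fruit". Item 6 asks for an amount: "Not counting carrots, potatoes, or salad, how many servings of other vegetables do you usually eat". All six have the same answer line, "Times/day _____ OR Times/week". Item 1 alone carries sample answers in brackets: "for example, once a day, three times a week, twice a month".

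On analysis, the SAP says: "Other secondary, continuous outcome measures will be analyzed with a one-way repeated measures ANOVA or Mann-Whitney Test", covering baseline to six months, and adds correlations and multivariable regression. Neither the SAP nor the protocol's Statistics section says how the six diet items are scored, summed, brought to a common period or combined with the other CANHEART parts. By contrast, Appendix 8 prints a scoring formula for the Godin questionnaire.

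**The concern.** A stem that asks for an amount above a box that asks for a frequency leaves the respondent to choose the unit. The answer is a bare number, so the choice is not recorded and cannot be reconstructed at analysis.

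Three features of this study give the ambiguity some weight:

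- Large-study participants follow links to Survey Monkey on eight occasions, and the protocol describes no staff contact for those surveys at which the item could be explained.
- The design is a single-group time series. If the way people read item 6 shifts between surveys, the shift appears as change, and there is no control group against which to subtract it.
- The SAP plans correlations and regressions. These use differences between people, which are affected even if each person reads the item the same way every time.

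At stake is the interpretability of one item in a secondary outcome that serves objective 2.

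**Working it through.** The documents give no figure for this measure, so there is no stated number to reproduce. The check compares stems with answer lines and then does simple unit arithmetic.

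**Stem against answer line (Appendix 8, fruit and vegetable part)**

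| Item | Unit asked for | Unit of the answer line | Agree? |
|---|---|---|---|
| 1 to 5 | frequency | times per day or per week | yes |
| 6 | servings | times per day or per week | no |

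**Size of the ambiguity for one person on item 6.** Let *f* be occasions per day and *s* servings per occasion. A times reader enters *f*; a servings reader enters *f* × *s*. The gap is *f* × (*s* − 1) per day. The documents give neither *f* nor *s*, so both are assumed over a range:

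| *f* per day | *s* = 1 | *s* = 1.5 | *s* = 2 | *s* = 3 |
|---|---|---|---|---|
| 0.5 | 0 | 0.25 | 0.5 | 1.0 |
| 1 | 0 | 0.5 | 1 | 2 |
| 2 | 0 | 1.0 | 2 | 4 |

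The gap vanishes when each occasion is one serving.

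**What this does to each kind of comparison**, taking *s* = 2:

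- Between people: two people with the same diet (*f* = 1) can be recorded as 1 and 2.
- Within a person, same reading, unchanged diet: no false change.
- Within a person, same reading, changed diet: going from once to twice a day is 1 to 2 (change 1) for a times reader and 2 to 4 (change 2) for a servings reader. A larger portion at the same frequency registers only for the servings reader.
- Within a person, reading switches from times to servings, unchanged diet: 1 becomes 2, a false increase of 1 per day. The reverse switch gives a false decrease of 1.

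**The monthly example in item 1.** A month is 365.25 / 12 / 7 = 4.348 weeks, so twice a month is 2 / 4.348 = 0.46 per week, or 0.46 / 7 = 0.066 per day. Entered in the weekly box as a whole number, the error per day is:

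- entered as 0: (0 − 0.46) / 7 = −0.07
- entered as 1: (1 − 0.46) / 7 = +0.08
- entered as 2: (2 − 0.46) / 7 = +0.22

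The box is an open blank, so a fraction is possible and the error is then avoidable.

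**The case against.** The best case against raising this is that it is a copy-editing slip in one item of a secondary questionnaire. The wording is the same at all eight surveys, so most people may read it the same way each time, and switches in opposite directions would tend to cancel. The questionnaires are completed online, whereas Appendix 8 is laid out as a paper form; the documents do not show the online answer fields. Item 6's weight in cardiovascular risk is also unknown, because no rule for combining the CANHEART parts is given. Finally, CANHEART is a named instrument, and rewording its stem could cost comparability with other uses of it.

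Most of this stands, and it keeps the severity low. It does not remove the defect. Consistent reading protects only a person whose diet does not change; it does not make two readers' values comparable. The appendix is also the only version of the item in the plan, so it is the version to correct. The point about the named instrument bears on which remedy to prefer.

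**Conclusion.** The mismatch in item 6 is real and should be corrected, at low severity. A recorded value for that item has no determinable unit. The consequences are blurred between-person comparisons, distorted change if the reading shifts, and mixed units if the items are summed. For one person eating other vegetables once a day, the ambiguity runs from 0 to 2 per day under an assumed 1 to 3 servings per occasion. Its effect on the study's results cannot be estimated from the documents. The primary outcome and the sample size are unaffected.

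A reader might infer more than the documents support:

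- *That the plan adds unlike units.* No six-item total or CANHEART score is defined, so this would happen only if someone summed the items.
- *That diet is the only part of objective 2 able to show graded change.* The tobacco part also records an average daily number for users.
- *That a false change of a stated number of standard errors should be expected.* This would need servings per occasion, the net share of people switching reading, the SD of change and the number of completers who answer the item. The documents supply none of these, and they give no reason for switching to run in one direction.
- *That the monthly example seriously damages the whole section.* It sits inside item 1 only, and a zero or fraction can be entered in the weekly box. A large error across all six items would need the same entry mistake on every one.

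**What to change.** 1. Make item 6's stem and boxes use one unit. The preferred change is to relabel its boxes *Servings/day OR Servings/week*, which leaves the stem of the named instrument as it is. The alternative is to reword the stem to ask how often other vegetables are eaten, at the cost of departing from that wording and losing the amount.
2. State in the SAP how the diet items are scored: convert every item to a per-day figure, and do not count item 6 servings as times in any total. Report item 6 separately, or show the total with and without it. The same reporting rule serves for any answers already collected under the present wording.
3. Minor: add a *Times/month* box or drop the monthly example from item 1.

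The cost is a label change in item 6 at each of the eight online surveys, one optional box or deletion, and a sentence or two in the SAP. The label change should reach all eight surveys together, so that a participant does not meet two versions of the item.
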